6.5.6 Pregnancy and assessments of fertility

Serum pregnancy test will be performed for all women by the central laboratory as detailed in Table 6-1. Patients becoming pregnant will be recommended to interrupt the study drug. Additional pregnancy testing may be performed at the investigator's discretion during the study.

Confidential

Novartis

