dose of fingolimod, macular edema, hypertension, dyspnea, bronchitis, and diarrhea. The AEs most prominently associated with fingolimod treatment (eg, liver enzyme elevations, bradycardia, and macular edema) appeared to show a dose response. There were no AEs that appeared to be specifically related to long-term treatment with fingolimod.

- In general, the AE profile of fingolimod in MS patients did not depend on gender, age, or previous treatment with disease-modifying drugs. The only exception was liver enzyme elevations, which were more frequent in male patients than in female patients treated with fingolimod.
- The overall incidence of infections, including serious infections, was similar in the fingolimod treatment groups and the comparator arms (IFN or placebo) in both completed Phase III studies. A slightly higher frequency of lower respiratory tract infections (primarily bronchitis) was observed in fingolimod-treated patients, with an apparent dose effect. The current data showed no clear relationship between lymphocyte count and the incidence of infections on fingolimod treatment.
- The accumulated data from the MS program do not show an association of fingolimod therapy with the development of malignancies. In the FREEDOMS study, more cancers were seen in the placebo group than in the treated groups. Incidence estimates for various forms of skin cancer (and other malignancies) from pooled safety data are comparable between treatment groups and placebo. There appears to be no increased risk with greater duration of exposure (Kappos et al., 2010).
- Initiation of fingolimod treatment has been associated with atrioventricular (AV) conduction delays usually as first-degree AV blocks (prolonged PR interval on electrocardiogram [ECG]). Second-degree AV blocks, usually Mobitz Type I (Wenckebach), have been observed in less than 0.5% of patients receiving fingolimod 0.5 mg in clinical trials. The conduction abnormalities typically were transient, asymptomatic, usually did not require treatment, and resolved within the first 24 hours on treatment.
- Data on the safe use of fingolimod in pregnancy or with breast-feeding are limited, although preclinical data suggest risk to the fetus and newborn is possible.

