The inclusion and exclusion criteria will be assessed at Screening and Randomization Visit (before patient is randomly assigned to treatment using an interactive voice response system [IVRS]). The results of all screening assessments must be available before randomization. A subject who is under screening but has not been enrolled due to failure to meet the inclusion criteria or failure to be randomized within the specified time per protocol, may be considered for re-screening if a change in the patient's medical status or a modification of the study's eligibility criteria makes the patient potentially eligible. Re-screening will be allowed on a case-by-case basis upon approval by the study Medical Monitor. A new informed consent form should be signed in case of re-screening and a new number will be assigned to the subject. The required re-screening procedures should be discussed with the Medical Monitor.

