 - history of substance abuse (drug or alcohol) in the past 5 years or any other factor (i.e., serious psychiatric condition) that may interfere with the patient's ability to cooperate and comply with the study procedures
 - progressive psychiatric/neurological condition that may affect participation in the study
- 20. Patients who have received an investigational drug or therapy within 180 days or 5 half-lives of randomization, whichever is longer.
- 21. Patients with a history of hypersensitivity to any of the study drugs, to drugs of similar chemical classes, or to mannitol.

- 22. Pregnant or nursing (lactating) women, where pregnancy is defined as the state of a female after conception and until the termination of gestation, confirmed by a positive human chorionic gonadotropin laboratory test.
- 23. Women of child-bearing potential, defined as all women physiologically capable of becoming pregnant, UNLESS they are using highly effective contraception during dosing with study treatment. Highly effective contraception includes:
 - Total abstinence (when this is in line with the preferred and usual lifestyle of the patient). Periodic abstinence (e.g., calendar, ovulation, symptothermal, post-ovulation methods) and withdrawal are not acceptable methods of contraception.
 - Female sterilization (have had surgical bilateral oophorectomy with or without hysterectomy) or tubal ligation at least 6 weeks before taking study treatment. In case of oophorectomy alone, only when the reproductive status of the woman has been confirmed by follow up hormone level assessment.
 - Male partner sterilization (at least 6 months prior to Screening). For female patients on the study, the vasectomized male partner should be the sole partner for that patient.
 - Use of oral, injected, or implanted hormonal methods of contraception or other forms of hormonal contraception that have comparable efficacy (failure rate <1%), for example, hormone vaginal ring or transdermal hormone contraception, placement of an intrauterine device or intrauterine system.

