6.5.5 Ophthalmologic examinations and optical coherence tomography

An ophthalmic examination will be performed to screen for macular edema as described in Table 6-1 and Table 6-2 for patients that discontinued study drug. An optical coherence tomography (OCT) and fluorescein angiography (FA) will be done only if needed to confirm macular edema. If there is a suspicion of macular edema at Screening, an OCT and FA should be performed to confirm the diagnosis. If the diagnosis is confirmed, the patient should be deemed a screening failure and should not be randomly assigned.

Patients with a history of or newly diagnosed uveitis after initiation of study drug may require more frequent ophthalmic evaluations. Refer to the Guidance for Ophthalmic Monitoring (Appendix 4) for details on monitoring of patients with uveitis during the study.

Study drug must be discontinued in any patient who has a diagnosis of macular edema confirmed by OCT and FA.

Patients with a diagnosis of macular edema must be followed up monthly and more frequently if needed based on the ophthalmologist's judgment. Further ophthalmologic evaluations will be conducted until such time as resolution is confirmed or no further improvement is expected by the ophthalmologist (based on a follow-up period of not less than 3 months). If the patient does not show definite signs of improvement on examination by specialized testing (e.g., OCT) 6 to 8 weeks after discontinuation of study drug, then therapy for macular edema in conjunction with an ophthalmologist experienced in the management of this condition should be initiated.

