Appendix 3: Guidance on safety monitoring

Patients whose blood pressure reading is \geq 140 (systolic) and/or \geq 90 mm Hg (diastolic) should have their blood pressure retested after 15 minutes of rest. If the blood pressure is still elevated, they should be followed up in one month by an unscheduled visit if the scheduled visit is not due. Should systolic BP \geq 140 and/or diastolic BP \geq 90 mm Hg values be confirmed at the second visit, the patient should be referred to his primary care physician, an independent internist or to the specialty hypertension clinic for evaluation, diagnosis and treatment of hypertension.

Patients with BP values of >160/100 mm Hg (confirmed by repeat testing) at any visit during the study should be immediately referred as above for evaluation, diagnosis and treatment of hypertension.

Newly diagnosed hypertension as well as an aggravation of a preexisting condition must be reported as an AE and appropriate antihypertensive medication/dosage adjustment must be considered by the investigator.

Guidance on monitoring of patients with elevated liver function tests

In case of detection of elevated ALT/AST values >2 and <5 times the ULN range, additional blood chemistry panel including ALT, AST, AP, GGT, total and conjugated bilirubin, albumin may be performed at the investigator's discretion.

If ALT/AST values reach 5 times the ULN, confirmed upon repeat testing within two weeks of the initial result or sooner at the discretion of the investigator, the study drug must be permanently discontinued. Patients who develop symptoms suggestive of hepatic dysfunction such as unexplained vomiting or jaundice, should have liver enzymes checked and fingolimod should be discontinued if significant liver injury is confirmed.

In case of isolated elevation of bilirubin over 2.0 mg/dl (34.2 umol/L) unless in context of Gilbert's syndrome, confirmed upon repeat testing within two weeks of the initial result, the investigator must discontinue the study drug. Additional evaluations may be performed at the discretion of the investigator.

For any unscheduled laboratory assessments performed locally, an identical sample should also be sent to the central laboratory for analysis and capture in the central database.

An interruption or discontinuation of the study drug should be clearly documented and reflected on Dosage Administration Record CRF. AE/SAEs need to be filed as appropriate.

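### When a patient becomes pregnant on fingolimod, Section 6.5.6 only recommends interrupting study drug; no visible text makes stopping mandatory or bars dispensing or restart

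*Protocol*

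**What the plan says.** The only visible instruction about study drug after a patient becomes pregnant is in Protocol Section 6.5.6: "Patients becoming pregnant will be recommended to interrupt the study drug". The same section allows extra pregnancy tests at the investigator's discretion.

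Other parts of the protocol bear on it:

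- Section 1.1 says data in pregnancy are limited and that "preclinical data suggest risk to the fetus and newborn is possible".
- Section 4.2, exclusion 22, bars pregnant women, with pregnancy "confirmed by a positive human chorionic gonadotropin laboratory test". Exclusion 23 bars women of child-bearing potential "UNLESS they are using highly effective contraception during dosing with study treatment".
- Section 4 says when these criteria are checked: "The inclusion and exclusion criteria will be assessed at Screening and Randomization Visit".
- Table 6-1 schedules a urine dipstick at Visits 2 to 7 and at follow-up, with no action tied to a positive result.
- Section 5.5.6 leaves interruption and restart to the investigator's judgment. Pregnancy is not among its listed conditions.
- Section 7.3 requires a report to the sponsor within 24 hours and follow-up of the outcome. It does not mention study drug.

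**The concern.** The protocol treats pregnancy as a bar to entry and requires highly effective contraception while a patient is dosed. Once a pregnancy occurs on study, the instruction becomes advice to the patient. It puts no explicit duty on the site to withhold capsules. Because it speaks of interrupting, it also leaves open when drug may resume.

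The stake is fetal exposure to fingolimod after the pregnancy is known, which exclusions 22 and 23 exist to prevent. The 24-hour report in Section 7.3 makes the pregnancy known to the sponsor but does not in itself end the exposure. This is a safety-conduct point. No estimate, error rate or power figure in the plan depends on it.

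**Working it through.** **Is there a mandatory rule elsewhere in the visible text?** The protocol sections where one would be expected are:

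- 5.5.2 and 5.5.4 (dispensing): no mention of pregnancy.
- 5.5.6 (interruption and restart): investigator judgment, pregnancy not listed.
- 5.5.9 (prohibited treatment) and 5.5.10 (discontinuation and withdrawal): no mention.
- 7.3 (pregnancies): reporting and follow-up only.
- Appendices 3 and 4 (safety and ophthalmic monitoring): no pregnancy rule.

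The SAP contains none either. Exclusion 22 prevents a first dose in a woman already known to be pregnant, so the gap concerns pregnancy arising after randomization.

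**How does the wording compare with other risks in fingolimod patients?**

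| Strength | Risk | Place |
|---|---|---|
| Must stop | Macular edema: "Study drug must be discontinued in any patient who has a diagnosis of macular edema confirmed by OCT and FA" | 6.5.5 |
| Must stop | Confirmed ALT/AST at 5 times ULN: "the study drug must be permanently discontinued" | Appendix 3 |
| Must stop | Confirmed isolated bilirubin over 2.0 mg/dL, outside Gilbert's syndrome: "the investigator must discontinue the study drug" | Appendix 3 |
| Must interrupt, with a restart condition | Lymphocytes below 0.2 x 10^9/L with signs of infection | Appendix 3 |
| Should stop | New skin cancer | 6.5.10 |
| Should stop | FEV1, FVC or DLCO below 60% of baseline | Appendix 3 |
| Should stop | Hepatic symptoms with confirmed significant liver injury | Appendix 3 |
| Suspension should be considered | Serious infection | Appendix 3 |
| Patient is recommended to interrupt | Pregnancy | 6.5.6 |

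Pregnancy falls below the must and should groups. The lymphopenia rule shows that the protocol can also state a restart condition when it wants one.

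**How much drug does one dispensing supply?** Inputs:

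- Dosing is once daily, and each dispensing lasts to the next scheduled visit (5.5.4).
- Dipstick and dispensing coincide after Day 1 at Visits 3, 4, 5 and 6, that is Months 1, 3, 6 and 9 (Table 6-1).
- The visit window is ±5 days (Table 6-1).
- One month is 30 days (SAP 3.8.1).

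Results:

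- Month 1 to 3: 2 x 30 = 60 doses. With ±5 days at each end, 50 to 70.
- Months 3 to 6, 6 to 9 and 9 to 12: 3 x 30 = 90 doses each. With the windows, 80 to 100.
- One dispensing after a positive test: 50 to 100 doses.
- All four dispensings: 60 + 3 x 90 = 330 doses.

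**What would holding drug after a false-positive dipstick cost?** Central results come no sooner than 48 hours after receipt (6.5.3). With shipping assumed at 1 to 4 days, the shortest hold is 2 + 1 = 3 to 2 + 4 = 6 days. It could be longer, because 48 hours is a floor. Section 5.5.6 requires repeat 6-hour monitoring at restart in three cases:

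- Treated 14 days or less: off drug 1 day or more.
- Treated more than 14 and less than 29 days: off drug more than 7 consecutive days.
- Treated 4 weeks or more: off drug more than 14 consecutive days.

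The first scheduled dipstick after Day 1 can fall no earlier than day 30 - 5 = 25, so a hold of 3 to 6 days at a scheduled visit stays under the 7-day and 14-day limits. A discretionary test in the first 14 days would not: any hold of a day or more would trigger monitoring at restart.

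**The case against.** A rule does exist, and the dispute is over its strength. The site is bound to give the recommendation, and Section 11 permits no authorized deviations, so an investigator who supplied drug without giving that advice would already be off protocol. Continued exposure needs someone to dispense or restart against the advice. Contraception is required throughout dosing, urine tests are done at every visit from Visit 2, the sponsor hears of each pregnancy within 24 hours, and the investigator may stop drug at any time. All of this stands, and it makes the event unlikely. It does not supply a visible rule that continued dosing would break once the advice had been given.

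A reader might infer that pregnancy is singled out against a general convention of mandatory stopping. The documents do not support that: several serious risks carry should, and serious infection carries only consideration of suspension. What can be said is that the pregnancy wording is weaker than the must and should rules and sits badly with exclusions 22 and 23.

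A reader might also infer that the plan contains no mandatory rule anywhere. That goes too far. Section 6.5.7, directly after the quoted text, is not shown, and the consent pages are removed. A rule could sit there, although Section 6.5.6 reads as complete in itself.

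**Conclusion.** The point holds for the visible text. Stopping fingolimod in a known pregnancy is recommended but not required, and neither dispensing nor restart is barred. The change is worth making on safety grounds, with medium confidence because adjacent text is hidden.

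No frequency can be stated, since the documents give no pregnancy rate. The exposure per event is about 50 to 100 daily doses for one dispensing after a positive test, assuming 30-day months and supply that just reaches the next visit. The 330-dose total is a ceiling and should not be read as an expected exposure. It needs a positive test at Month 1 and four successive dispensings against advice, and it runs to Month 12 whatever the course of the pregnancy.

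**What to change.** Replace the sentence in Section 6.5.6 with a rule of this kind:

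> For patients in the fingolimod arms, study drug must be stopped when pregnancy is confirmed, must be held after a positive urine dipstick until the confirmatory test is known, and must not be dispensed or restarted during pregnancy.

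The confirmatory test can be the laboratory hCG test already named in exclusion 22. State the same rule in Section 5.5.6 as a separate mandatory sentence, outside the list of conditions left to judgment, and cross-reference it from Section 7.3. Do not add pregnancy to the withdrawal reasons in Section 5.5.10: patients who stop drug stay in the study under Table 6-2. An arm-specific rule does not break the dose blind, because it covers both fingolimod doses and the treating physician already knows who receives injections (Section 5.4).

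The cost is wording in three sections and a confirmatory test that Section 6.5.6 already permits. A false positive costs at least 2 days of dosing plus shipping, possibly more, and repeat 6-hour monitoring if the hold falls in the first 14 days of treatment. A few more patients may go off drug. The effect on the primary analysis is small, since Section 9.4.3 counts relapses whether or not the patient is on drug.

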6.5.8 Chest x-ray

This section is no longer applicable after the changes made at protocol amendment 2.

6.5.9 Pulmonary function tests

Pulmonary function tests evaluating FEV₁, FVC, and D_LCO will be performed at Screening, Month 6, Month 12, End of Study, and 3 months after study drug discontinuation as indicated in Table 6-1 and Table 6-2. This test will be conducted in all patients who are enrolled into the study and in the manner consistent with the standard pulmonary laboratory practice.

Any condition that might affect the outcome of PFTs including infection, respiratory symptoms, occupational exposures (including asbestos), and cigarette smoking, needs to be collected before every PFT testing and transcribed to the PFT eCRF page.

Patients who discontinue study drug due to respiratory AE(s) should be evaluated by a pulmonary specialist and further investigations (e.g., PFTs, chest x-ray or HRCT, biopsy) should be performed as needed.

Spirometry

The technician should demonstrate the appropriate technique to the patient and follow the standard procedure. The quality of the tests must be accounted for including the technicians' comments (especially when, despite proper coaching of the patient, full collaboration cannot be achieved). The FEV_1/FVC ratio will be calculated centrally by the trial statistician.

A minimum of 3 acceptable maneuvers will be performed at each visit. The acceptability criteria are a satisfactory start of test and a satisfactory end of test. In addition, the technician should observe that the patient understood the instructions and performed the maneuver with a maximum inspiration, a good start, a smooth continuous exhalation, and maximal effort. The largest FVC and the largest FEV₁ will be recorded, after examining the data from all of the acceptable curves, even if the 2 values do not come from the same curve. Please refer to the American Thoracic Society/European Respiratory Society guidelines for standardization of spirometry (Miller et al, 2005a; Miller et al, 2005b) and single breath determination of carbon monoxide uptake in the lung (MacIntyre et al, 2005).

If for any reason a patient is permanently discontinued from study medication the patient will have PFTs performed at his last visit or within 30 days of the study drug discontinuation. Refer to Appendix 3 for Guidance on monitoring patients with pulmonary function safety concern.

Forced expiratory volume in 1 second (FEV₁):

The FEV_1 describes the volume (in Liters) that is expelled within one second of forced expiration after a maximal inspiration and reflects the large airway resistance. A decrease in FEV_1 serves as a good parameter for detection of an obstructive ventilatory defect.

Forced vital capacity (FVC):

The FVC denotes the volume of gas (in Liters) which is exhaled during a forced expiration starting from a position of full inspiration and ending at complete expiration. This parameter

is normal or might be slightly decreased in obstructive disease but shows a mild to severe decrease in restrictive disease.

Page 64

Diffusion capacity of carbon monoxide (D_I CO):

Gas exchange is assessed by the D_ICO evaluated by the single breath holding method. It is a measurement of carbon monoxide (CO) transfer from the lung to pulmonary capillary blood over a breath-holding period. Due to ability of CO to bind to hemoglobin, the diffusion capacity needs to be corrected for hemoglobin to reflect an altered lung gas transport rather than altered hemoglobin.

The average of at least 2 acceptable tests that meet the repeatability requirement of either being with 3 mL CO/min/mm Hg (or 1 mmol/min/kPa) of each other or being within 10% of the highest value should be reported.

A D_ICO test is acceptable if it fulfills all the following criteria:

- Use of proper quality-controlled equipment
- Inspired volume of greater than 85% of largest vital capacity in less than 4 seconds
- A stable calculated breath hold for $10 (\pm 2)$ seconds. There should be no evidence of leaks or Valsalva or Mueller maneuvers
- Expiration in less than 4 seconds (and sample collection time less than 3 seconds), with appropriate clearance of dead space and proper sampling/analysis of alveolar gas

All values must be corrected for hemoglobin concentration in the study.

The D_LCO is usually expressed in European CI conventional units: mL CO/min/torr (or mL CO/min/mm Hg), whereas the US mainly uses SI units: mmol CO/min/kPa (Conversion factor: SI units \times 2.986 = CI units).

6.5.10 **Dermatological examination**

A dermatologist will complete a dermatological examination as outlined in Table 6-1 and Table 6-2 to support monitoring of patients for the potential development of new skin cancers during the study. For patients who discontinue treatment early, a dermatological examination should be performed at end of study. Study drug should be discontinued in patients who develop a new skin cancer during the study.

6.5.11 **Columbia-Suicide Severity Rating Scale**

The C-SSRS, is a semi-structured interview designed to systematically assess and track suicidal AEs (behavior and ideation) throughout different settings including clinical studies.

The C-SSRS captures the occurrence, severity, and frequency of suicide-related thoughts and behaviors. The C-SSRS will be administered by an IVRS with the patient entering responses directly into the IVRS. Caregivers will not be allowed to answer the C-SSRS questions on behalf of the patient. Sites must review reports received from the system for any answers indicative of suicidal ideation and AEs. Adverse events ascertained through the administration of the C-SSRS will be documented. This scale was developed by researchers at Columbia University and will be administered in this study as specified in the assessment schedules

(Table 6-1 and Table 6-2). In case the score is 4 or above, the patient must be referred to the health care professional for further assessment and/or treatment.

